### **Additional Analyses**

Each of the two response criteria that is a component of the primary endpoint, i.e., (1) MBL volume of < 80 mL at the Final Month; and (2) 50% or greater reduction in MBL volume from Baseline to the Final Month will be analyzed separately in the same way as for the primary analysis. Baseline and Final Month MBL volumes obtained for the primary analysis via MI will be used. The number and percentage of subjects meeting each criterion at the Final Month will be summarized by treatment group. The comparison between the elagolix treatment group and placebo will be made using a logistic regression model including treatment as the main effect and Baseline MBL volume as a covariate.

Besides the method in the primary analysis, the number and percentage of subjects meeting each criterion at the Final Month will also be analyzed in the same way as in each sensitivity analysis for the primary endpoint.

The number and percentage of subjects satisfying either (1) MBL volume < 80 mL, or (2) 50% or greater reduction in MBL volume from Baseline, or both will be summarized for every 28-day interval by treatment group based on observed MBL volume. This summary will also be provided at Final Month of the Treatment Period for subjects who prematurely discontinue study drug due to "lack of efficacy," or "requires surgery or invasive intervention for treatment of uterine fibroids" as the primary reason. Cross-tabulation of the two bleeding criteria above for each 28-day interval in the Treatment Period will be provided by treatment group based on observed MBL volume.

Plots will be provided by treatment group using the MBL volume data for the primary analysis (after multiple imputation):

- Proportion of responders at Final Month.

Additional supportive analysis of the primary efficacy endpoint using Bayesian historical borrowing may be explored. Historical data of placebo subjects from AbbVie M12-815 and M12-817 studies may be incorporated in the analysis based on the consistency and similarity between historical placebo data and current placebo data. Details of the historical borrowing method are provided in [Appendix D](#).

## 8.4 Additional Efficacy Analyses

### MBL Volume

The change and percent change from Baseline to the Final Month in MBL volume obtained from the primary analysis after multiple imputation will be summarized by treatment group and compared between the elagolix treatment group and placebo, using one-way ANCOVA with treatment as the main effect and Baseline MBL volume as a covariate. Baseline and Final Month MBL volumes obtained for the primary analysis will be used.

The comparison of change or percent change from Baseline in MBL volume to each month between the elagolix treatment group and placebo will be performed using a Mixed Model Repeated Measures (MMRM) model with observed MBL volume, as described in [Section 8.2](#).

For the analysis above using observed MBL volume in each 28-day interval, only subjects who did not prematurely discontinue in or before this 28-day interval will be included. For example, for Study Days 29 – 56, it includes subjects who were on treatment for at least 56 days.

Plots will be provided by treatment group using the MBL volume data for the primary analysis (multiple imputation):

- Cumulative distribution function for MBL volume at Final Month;

- Cumulative distribution function for percent reduction from Baseline to Final Month in MBL volume;
- Cumulative distribution function for reduction from baseline to Final Month in MBL volume.

Plots will be provided by treatment group using observed MBL volume data:

- Mean change from Baseline in MBL volume over time.

### **Amenorrhea**

The number and percentage of subjects who achieve amenorrhea will be calculated for each treatment group. The amenorrhea analysis includes subjects on study drug for at least 38 days. For each subject, amenorrhea at the Final Month is defined as having 0 days of bleeding or spotting during the last 28 days prior to and including the last dose day, with the interval starting at or beyond Study Day 11. If a subject does not have evaluable AH data during the last 28 days and no bleeding or spotting or "There was no visible blood on the sanitary products" is indicated on UBQ, then she is considered amenorrheic. The denominator will be the number of subjects with at least 38 days on study drug and having an amenorrhea status at the Final Month. The number and percentage of subjects with amenorrhea at Final Month will be summarized by treatment group and compared between the elagolix treatment group and placebo using the Miettinen-Nurminen (M-N) method.

Time to amenorrhea is defined as the number of days from the first study drug dose date to the day a subject achieves amenorrhea (i.e., the day a subject achieves amenorrhea – the first study drug dose date + 1). For a subject who achieves amenorrhea, the day she achieves amenorrhea is defined as the next day of the last bleeding/spotting day during the Treatment Period. The median, Q1, and Q3 of time to amenorrhea will be calculated for subjects who achieve amenorrhea using Kaplan-Meier method.

In the monthly analysis of bleeding for amenorrhea, the numerator will be the number of subjects on treatment who do not bleed or have spotting during the specified time window specified in [Table 1](#) (but may have begun bleeding or spotting thereafter) and the denominator will be the number of subjects on study drug for the full window and having an amenorrhea status for that month.

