## **4.0 Analysis Populations**

The following population sets will be used for the analyses.

The full analysis set (FAS) is composed of all randomized subjects who have received at least 1 dose of study drug in this study. The data from the FAS will be presented by the treatment group assigned at the time of randomization, even if a subject does not receive the correct treatment or does not follow the protocol until completion. The FAS will be used for all baseline and efficacy analyses.

The Safety Analysis Set includes all randomized subjects who received at least 1 dose of study drug. The data from the safety analysis set will be presented by the treatment actually received regardless of which treatment group was assigned at the time of randomization. If a subject takes more than 1 treatment, the subject will be analyzed in the safety analysis set as taking the treatment to which she is randomized. All safety analyses will be performed based on Safety Analysis Set.

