## **8.0 Efficacy Analyses**

### **8.1 General Considerations**

All efficacy analyses will be conducted in the FAS Population. All tests will be 2-sided at an alpha level of 0.05.

Unless otherwise specified, categorical data will be summarized by frequency and percentage; descriptive summaries of continuous data will display the mean, SD, median, minimum, and maximum.

For continuous variables, when the analyses of change and/or percent change from Baseline to post-baseline visit(s) are performed, the within-group change from Baseline to each applicable visit will be summarized by treatment group with the mean, SD (or SE), and 95% Confidence Intervals (CIs). The between-group differences will be summarized with the mean, SE, 95% CIs, and P value when applicable. At each post-baseline visit, the Baseline mean and post-baseline visit mean will be calculated for all subjects with baseline and post-baseline value at that visit by treatment group.

Final Month is defined as the last 28 days prior to and including the last dose day.

Unless otherwise specified, there is no hypotheses testing for efficacy endpoints in the Post-Treatment Follow-up Period.

Information regarding corresponding statistical methods for analyses and any additional statistical measures required for a specific variable/endpoint will be provided in relevant sections.

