### **Suppression of bleeding**

Suppression of bleeding is defined similarly to amenorrhea except that spotting is allowed. For each subject, achieving suppression of bleeding at the Final Month is defined as having 0 days of bleeding (spotting allowed) during the last 28 days prior to and including the last dose day with the interval starting at or beyond Study Day 11. The

suppression of bleeding analysis includes subjects with at least 38 days on study drug. If a subject does not have evaluable AH data during the last 28 days and no bleeding is indicated on UBQ ("Subject only had spotting that did not require the use of sanitary products" or "There was no visible blood on the sanitary products" is allowed), then the subject will be considered having achieved suppression of bleeding. The denominator will be the number of subjects with at least 38 days on study drug and having a suppression of bleeding status at the Final Month.

The number and percentage of subjects achieving suppression of bleeding at Final Month will be summarized by treatment group and compared between the elagolix treatment group and placebo using the Miettinen-Nurminen (M-N) method.

Time to suppression of bleeding is defined as the number of days from the first study drug dose date to the day a subject achieves suppression of bleeding (i.e., the day a subject achieves suppression of bleeding – the first study drug dose date + 1). For a subject who achieves suppression of bleeding, the day she achieves suppression of bleeding is defined as the next day of the last bleeding day during the Treatment Period. The median, Q1, and Q3 of time to suppression of bleeding will be calculated for subjects who achieve suppression of bleeding using Kaplan-Meier method.

Monthly analysis of bleeding for suppression of bleeding, incidence and cumulative incidence of suppression of bleeding will be provided in the same way as will be done for amenorrhea in [Table 1](#) and [Table 2](#). Plots will be provided by treatment group for percentage of subjects with incidence and cumulative incidence of suppression of bleeding during the Treatment Period, respectively.

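### Final Month amenorrhea and suppression of bleeding are compared only in women with at least 38 days on drug and a known status; no full-FAS comparison is planned and the exception to the FAS rule is not flagged

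*SAP*

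**What the plan says.** SAP 4.0 defines the FAS as "all randomized subjects who have received at least 1 dose of study drug in this study", with no minimum time on treatment, and adds: "The FAS will be used for all baseline and efficacy analyses". SAP 8.1 repeats the rule: "All efficacy analyses will be conducted in the FAS Population". Neither sentence carries an exception.

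SAP 8.4 sets a narrower group for two endpoints.

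- **Amenorrhea.** "The amenorrhea analysis includes subjects on study drug for at least 38 days". The window is the 28 days ending on the last dose day, "with the interval starting at or beyond Study Day 11". The denominator is the "number of subjects with at least 38 days on study drug and having an amenorrhea status at the Final Month".
- **Suppression of bleeding.** The window condition is the same, and the denominator is the "number of subjects with at least 38 days on study drug and having a suppression of bleeding status at the Final Month".

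Both endpoints are compared between arms at the Final Month by the Miettinen-Nurminen method. If alkaline hematin data are not evaluable, an answer on the Uterine Bleeding Questionnaire (UBQ) can supply the status. Protocol 3.3 lists both as proportions of subjects, with no 38-day condition.

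**The concern.** Staying on drug to Day 38 and having a known status are both determined after randomisation. A dosed woman who fails either condition is removed from numerator and denominator, where she could have been counted as not achieving the outcome. The groups compared are then subsets of the randomised arms, and early stopping may differ between drug and placebo.

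The SAP treats the same women differently for the primary endpoint. There, a woman whose last dose is on Day 1 stays in, with her Final Month volume imputed from Month 1 (SAP 8.3.3). Stopping for lack of efficacy or for surgery counts as non-response (8.3.1), and a non-responder imputation (NRI) analysis is planned (8.3.4). A woman who stops on Day 30 for lack of efficacy is thus a primary non-responder, but absent from the amenorrhea and suppression rates.

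The loss would also be hard to see. No count of excluded women is specified for these analyses, and the exposure categories in SAP 6.0 (1 to 28 days, over 28 to 56 days) straddle Day 38.

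**Working it through.** **1. Where the 38 days come from.** SAP 6.0 defines duration as last dose date minus first dose date plus 1, so 38 days on drug puts the last dose on Study Day 38. A 28-day window ending there starts on Day 38 - 28 + 1 = 11. The 38-day rule and the Day 11 rule are therefore one condition. Operations Manual 2.2 places the Baseline visit on cycle Days 1 to 10, so a plausible purpose is to keep the baseline menses out of the window. The SAP does not state a reason.

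**2. Who leaves and who stays.**

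| Woman in the FAS | Final Month comparison in 8.4 |
|---|---|
| Stops before Day 38, any reason | Left out |
| 38 days or more, status unknown after UBQ | Left out |
| 38 days or more, status known, including stops for lack of efficacy | Kept and scored |

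**3. Is there a full-FAS version elsewhere?** Multiple imputation, the non-responder rule and NRI are written for the primary endpoint. The monthly amenorrhea analysis requires the full monthly window on drug plus a known status. The cumulative incidence summary again requires 38 days and a Final Month status. No full-FAS version of either endpoint is planned.

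**4. Effect on one arm's rate.** The documents give no amenorrhea, suppression or early-stopping rate, so d below is assumed. With x achievers among n women, a fraction d dropped and no achievers among those dropped, the reported rate is x / [n(1 - d)] and the FAS rate is x / n. The ratio is 1/(1 - d).

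- d = 5%: 1/0.95 = 1.053, about 5% relative
- d = 20%: 1/0.80 = 1.25, 25% relative

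**5. Effect on the comparison.** The planned arm sizes are 32 and 16 (SAP 2.4). The counts of 10 and 1 women with amenorrhea are assumed, and no dropped woman is an achiever. P-values come from a two-sided score test of the Miettinen-Nurminen type.

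| Dropped (elagolix + placebo) | Rates | Difference (points) | p |
|---|---|---|---|
| None (FAS) | 10/32 = 31.3% vs 1/16 = 6.3% | 25.0 | 0.055 |
| 3 + 1 | 10/29 = 34.5% vs 1/15 = 6.7% | 27.8 | 0.046 |
| 6 + 3 | 10/26 = 38.5% vs 1/13 = 7.7% | 30.8 | 0.047 |
| 6 + 0 | 10/26 = 38.5% vs 1/16 = 6.3% | 32.2 | 0.023 |
| 0 + 4 | 10/32 = 31.3% vs 1/12 = 8.3% | 22.9 | 0.12 |

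Losing women from elagolix alone widens the difference; losing them from placebo alone narrows it. With equal fractions (6 + 3, d = 6/32 = 3/16 = 18.75%) the ratio of the rates is unchanged, and the difference grows by the same factor: 25.0 / 0.8125 = 30.8.

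**The case against.** The strongest defence is that the restriction belongs to the endpoint. A woman with fewer than 38 days on drug cannot have a 28-day window starting at Day 11 or later, so the outcome as defined cannot be assessed in her. SAP 8.1 leaves endpoint-specific methods to the later sections, and 8.4 states its denominators openly. Other FAS analyses, such as hemoglobin, PGIC-MB and UFS-QoL, also use available data only. All of this stands, and it makes a flat contradiction too strong a reading: being in the FAS does not place a woman in every denominator. What remains is an unflagged exception and a complete-status comparison with no full-FAS counterpart. The window also does not explain the separate known-status condition.

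Three further points stand in part.

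- A reader might infer that treatment failures in general vanish. They do not: failures with 38 days or more on drug and a known status stay in, and UBQ answers recover some missing statuses.
- A reader might take Appendix D's 28:14 out of 32:16 (12.5% lost) as the SAP's own value of d. It is an allowance for roughly 90% observed primary endpoint data, not a rate of stopping before Day 38 or of unknown status.
- Scoring every missing woman as a failure has its own bias and is harsher than the multiple imputation used for the primary analysis, where NRI is only a sensitivity analysis. This argues for adding the full-FAS version beside the existing one, not for replacing it.

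**Conclusion.** The point holds as a gap in the plan for two additional endpoints. The only Final Month between-arm comparison of each conditions on two post-randomisation events, despite the general FAS statement. An arm's rate is overstated by 5% to 25% relative if 5% to 20% of its women are dropped and none achieved the outcome. Both the range and the no-achiever assumption are ours, and the latter is the extreme case. The direction of bias in the difference depends on which arm loses more women and cannot be derived from the documents.

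Two stronger readings are not supported. The assumed example does not show significance flipping both ways: starting at 0.055, p falls below 0.05 in three cases and moves further above it in the fourth, with counts chosen close to the threshold. Nor is this an overstated Month 6 rate, because the Final Month is the last 28 days on drug whenever treatment ends; a full-FAS denominator would not make it a Month 6 rate. The protocol's summary of changes calls the study exploratory, and the primary analysis is unaffected.

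**What to change.** 1. In SAP 8.4, add a Final Month comparison of amenorrhea and of suppression with the full FAS as denominator, counting women with less than 38 days on drug or with unknown status as not achieving the outcome. This parallels the NRI analysis of the primary endpoint.
2. Keep the 38-day, known-status analysis and report beside it the number excluded per arm, split by reason (less than 38 days on drug; status unknown).
3. State in SAP 8.1 that this analysis is an exception to the FAS.

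The cost is SAP wording and one extra row per table, with no new visits or data. The added rates will probably be slightly less favourable than those from the restricted group.

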### 2.4 Sample Size Determination

Approximately 48 subjects will be randomly assigned (in a 2:1 ratio) to receive either elagolix 150 mg QD (N = 32) or placebo (N = 16). The sample size will provide at least 80% power to detect a difference between the elagolix 150 mg QD group and the placebo group in the percentage of subjects meeting the primary endpoint on MBL at the Final Month of the placebo-controlled Treatment Period, with a final MBL volume < 80 mL and a reduction in MBL volume of  $\geq 50\%$  from Baseline, assuming response rates of 10% for the placebo group and 55% for the elagolix 150 mg QD group with a 2-sided  $\alpha = 0.05$ . The above sample size was calculated using nQuery Advanced 8.1.

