#### **8.3.3 Primary Efficacy Analysis**

The primary analysis of the primary endpoint will be performed using the full analysis set population.

If a subject has missing observed Final Month MBL volume, the Final Month MBL volume will be imputed using multiple imputation as described in Section 8.2.

The primary analysis of the primary efficacy endpoint with multiple imputation will be carried out in the following steps:

1. **Multiple Imputation:** 30 "complete" datasets of monthly MBL volume from Month 1 to Month 6 will be generated using SAS PROC MI as described above. The following covariates will be used in the imputation model:
  - a. Baseline MBL volume

- b. Randomized treatment group
  - c. Baseline hemoglobin
  - d. MBL volume in prior months
  - e. Age of the subject at Baseline
2. **Impute Final Month MBL Volume:** In each of the 30 generated datasets, subject's missing Final Month MBL volume will be imputed using the MBL volume from the "complete" dataset with Month 1 – 6 MBL volume by looking at the corresponding month of the last dose day using analysis time window. Subjects whose last dose day are the same as Study Day 1 will have their Final Month MBL volume imputed using their Month 1 MBL volume.
3. **Impute Responder Status:** The responder status (yes/no) will be derived from "complete" (observed or imputed) Final Month MBL volume, using the criteria as described in Section 8.3.1. Subjects whose primary reason for prematurely discontinuing study drug is "lack of efficacy," or "requires surgery or invasive intervention for treatment of uterine fibroids" will be considered as non-responders.
4. **Analysis:** Each of the 30 imputed datasets will be analyzed separately using a logistic regression model including treatment as the main effect and Baseline MBL volume as a covariate to compare the elagolix treatment group to placebo.
5. **Pooling:** Estimates of the proportions of responders in each treatment group and the difference between the proportions from the 30 imputed datasets obtained from step 3 will be combined into one overall result using PROC MIANALYZE in SAS.

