### **PGIC on Menstrual Bleeding Questionnaire**

For PGIC on menstrual bleeding (PGIC – MB), the number and percentage of subjects in each response category will be summarized at each applicable visit by treatment group. Missing data will not be imputed. No statistical tests will be performed.

For PGIC – MB, the response categories of "Very Much Improved" and "Much Improved" will be combined and the remaining five categories of the PGIC scale will be combined and labeled "Otherwise." The number and percentage of subjects with response of (a) "Very Much Improved" or "Much Improved," and (b) "Otherwise" will be summarized at each applicable visit by treatment group. Comparisons will be made using the Miettinen-Nurminen (M-N) method for each applicable visit in the Treatment Period.

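### Final Month amenorrhea and suppression of bleeding are compared without Baseline MBL, so a chance baseline imbalance between arms of 32 and 16 goes uncorrected

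*SAP*

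**What the plan says.** The primary analysis (SAP 8.3.3) uses a "logistic regression model including treatment as the main effect and Baseline MBL volume as a covariate to compare the elagolix treatment group to placebo". SAP 8.3.4 uses the same model for the sensitivity analyses and for the two response components. Under MBL Volume in SAP 8.4, change to the Final Month is tested by ANCOVA with Baseline MBL, and monthly change by MMRM with a baseline covariate. Hemoglobin and UFS-QoL are adjusted for their own baselines.

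The binary bleeding endpoints are treated differently:

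- Amenorrhea at the Final Month is "compared between the elagolix treatment group and placebo using the Miettinen-Nurminen (M-N) method".
- For suppression of bleeding, "The number and percentage of subjects achieving suppression of bleeding at Final Month will be summarized by treatment group and compared between" the arms, by the same method.

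Neither text names a covariate or stratum or gives a reason for leaving one out. SAP 8.1 adds that "All tests will be 2-sided at an alpha level of 0.05".

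SAP 2.3, Protocol 5.8 and Operations Manual 3.23 and 6.3 describe the IRT randomisation and name no stratification factor. That is silence, not a statement that there is none.

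**The concern.** Both endpoints come largely from the alkaline hematin data behind the primary endpoint, with the bleeding questionnaire filling gaps. The plan treats baseline bleeding as worth adjusting for when it tests MBL response or MBL change, and then leaves it out here. With 16 women on placebo, the arms can differ noticeably in baseline bleeding by chance. If heavier bleeders are less likely to reach amenorrhea, that difference passes into the observed treatment difference. A reader facing a visible imbalance would have no prespecified adjusted result to consult.

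**Working it through.** **The plan's own figure.** SAP 2.4 states: "The sample size will provide at least 80% power to detect a difference", "assuming response rates of 10% for the placebo group and 55% for the elagolix 150 mg QD group". This is for the primary endpoint only.

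- Pooled rate: (16 × 0.10 + 32 × 0.55)/48 = 0.40.
- Null SE: sqrt(0.40 × 0.60 × (1/16 + 1/32)) = 0.150.
- Alternative SE: sqrt(0.09/16 + 0.2475/32) = 0.1156.
- Power: Φ((0.45 − 1.96 × 0.150)/0.1156) = Φ(1.35) = 91%.

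Exact power is 91.8% for Miettinen-Nurminen (M-N) and 86.5% for Fisher, so the statement holds. The plan gives no power or event rates for amenorrhea or suppression.

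**Chance of imbalance.** The standardised baseline difference has SE sqrt(1/32 + 1/16) = 0.306.

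- P(more than 0.25 SD) = 2 × (1 − Φ(0.25/0.306)) = 41%.
- P(more than 0.5 SD) = 2 × (1 − Φ(0.5/0.306)) = 10%.

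**Effect on the unadjusted test.** Simulated at 32:16 with a standardised normal baseline covariate and, by assumption, 30% events in both arms. The prognostic strength is also assumed and is therefore shown as a range.

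| Log-odds per SD | M-N type I error, all trials | M-N, imbalance > 0.5 SD | M-N stratified at the median, imbalance > 0.5 SD |
|---|---|---|---|
| 0.4 | 5.4% | 6.7% | about 5% |
| 0.7 | 5.4% | 8.9% | about 5% |
| 0.8 | about 5.5% | about 10% | 5-6% |
| 1.1 | 5.3% | 12.3% | about 6% |

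The overall rate stays near 5% because well-balanced trials reject less often (3.7% at 1.1 when the difference is under 0.25 SD). An imbalance of one SE (0.31 SD) moves the unadjusted risk difference by about 2 points at 0.4, 3-4 points at 0.7 and 4-6 points at 1.1.

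**Power of M-N stratified at the Baseline MBL median.** Event rates are assumed. Appendix D assumes 28:14 with observed primary data. That is a reasonable guide here, because these endpoints count only women with at least 38 days on drug and a known status.

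| Size, assumed rates | Unstratified | No effect | 0.8 | 1.1 | 1.5 | 2.0 |
|---|---|---|---|---|---|---|
| 32:16, 35% vs 5% | 69% | about 68% | 71% | 73% | 75% | 77-78% |
| 28:14, 35% vs 5% | 65% | 61% | 63% | 65% | 67% | 69% |
| 28:14, 45% vs 10% | 70% | 66% | 69% | 71% | 73% | 76% |

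**Logistic regression with continuous Baseline MBL.** The result depends on which test is taken from the model.

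- Score test: at 32:16 its power is within about 1 point of M-N when Baseline MBL predicts nothing. At 28:14 it costs about 1-2 points with no effect and gains about 3-7 at 1.1 log-odds per SD. Its type I error was about 5-6.5%.
- Wald test: at 35% vs 5% its power falls to 19-29%, with separation or near-separation in about 43% of trials.
- Likelihood-ratio test: type I error is about 8-9% when both arms have 10% events.

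**The case against.** The best case for the plan is that unadjusted M-N is a valid, prespecified test for sparse data. Randomisation keeps its average error near 5%. These are additional endpoints outside formal error control, in a study that the protocol's summary of changes calls exploratory. Baseline MBL will be tabulated by arm, and adjusted analyses of MBL volume are already planned. All of this stands. It makes the point small, but does not supply a prespecified adjusted result when an imbalance occurs.

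A reader might also infer more than the documents support:

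- **That the plan loses power.** The documents do not say how strongly Baseline MBL predicts these outcomes. At 28:14 the median-split test loses about 4 points if there is no effect, roughly breaks even near 1.1 log-odds per SD, and gains only beyond that.
- **That PGIC-MB has the same defect.** It is also unadjusted ("Comparisons will be made using the Miettinen-Nurminen (M-N) method for each applicable visit in the Treatment Period"), but it is a self-rated change item (Operations Manual 3.7), is not derived from MBL, and has no Final Month comparison.
- **That disagreement with the primary result would show imbalance.** These endpoints also differ in definition, denominator and missing-data handling. Moreover, step 5 of SAP 8.3.3 pools the responder proportions from step 3, before the logistic model, so the primary's reported rate difference is itself unadjusted as written.
- **That nothing else goes unadjusted.** The 8.5 subgroup summaries and the optional Bayesian analysis in Appendix D name no covariate either.

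**Conclusion.** The point holds for Final Month amenorrhea and suppression of bleeding, as a matter of interpreting results under an observed imbalance. It is not a validity defect. About one trial in ten of this size would have a Baseline MBL difference above 0.5 SD. In those trials the unadjusted test's error under the null is about 10-12% rather than 5-6%.

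This rests on 32:16 women, 30% events in both arms, a normally distributed covariate, and 0.8-1.1 log-odds per SD. At 0.4 the conditional error is only 6.7%. No unconditional loss of power is shown, and the primary analysis is untouched. Low priority, but cheap to settle before unblinding.

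**What to change.** In SAP 8.4, prespecify a Baseline-MBL-adjusted comparison for Final Month amenorrhea and suppression of bleeding, reported beside the unstratified M-N result.

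- **Preferred:** the score test for treatment from a logistic model with continuous Baseline MBL. Name the score test explicitly, since with few placebo events the Wald test loses power through separation and the likelihood-ratio test rejects too often.
- **Alternative:** M-N stratified at the Baseline MBL median, the split already defined in SAP 8.5.

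PGIC-MB can be left as it is, or given the same adjustment as an optional supportive analysis. State also whether the randomisation schedule is stratified.

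The programming cost is one covariate or stratum and one extra result per endpoint. If Baseline MBL is not prognostic, the statistical cost is about 0-2 points of power for the score test. For the median-split M-N it is about 1-2 points at 32:16 (2.5 at most in the scenarios run) and about 4 points at 28:14.
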